### 12.3.5. Normal Ranges

For the QT and QTcF parameters, the following categorizations will be done:

- of the actual values:
  - $\leq 450$  ms,
  - ]450,480] ms,
  - ]480,500] ms,
  - $>500$  ms;
- of the changes from baseline:
  - $\leq 30$  ms (including all decreases in QT),
  - ]30,60] ms,
  - $>60$  ms.

### 12.3.6. Analysis tables at Week 12

No formal inferential statistics (p-values) are planned in this SAP.

If the subject did not participate in the second period of the study, then the follow-up visit will be presented in the table of the first period of the study. If the subject participated in the second period of the study, then the follow-up value will be presented in the table of the second period of the study, not of the first period.

#### **Table 14.3.3.1: ECG up to Week 12: Descriptive statistics of the actual values per time point**

Descriptive statistics of the actual values per test and unit, and per treatment group.

Population: safety.

#### **Table 14.3.3.2: ECG at Week 12: Descriptive statistics of the changes from baseline**

Descriptive statistics of the changes from baseline per test and unit, and per treatment group. The actual value at baseline will also be presented in this table.

Population: safety.

#### **Table 14.3.3.3: ECG at Week 12: Shift table of the QT abnormalities**

Shift table per test, treatment group and time point. The table will present the shift in abnormality at each post-baseline time point (including the worst-case) versus the baseline abnormality. Parameters: QT and QTcF.

Population: safety.

**Table 14.3.3.4: ECG at Week 12: Treatment-emergent QT abnormalities**

Frequency table of the treatment-emergent abnormalities per parameter and treatment group. A post-baseline abnormality is considered treatment-emergent if it is higher than the baseline result. Parameters: QT and QTcF.

Population: safety.

**Table 14.3.3.5: ECG at Week 12: Treatment-emergent abnormal change in QT**

Frequency table per test and treatment group. The table will present the abnormality of the changes. Parameters: QT and QTcF.

Population: safety.

**Table 14.3.3.6: ECG up to Week 12: Frequency table of the eCRF ECG interpretation per time point**

Frequency table per treatment group of the ECG interpretation scores as recorded in the eCRF. Interpretation scores are:

- Normal ECG in sinus rhythm;
- Cardiac conduction disorders;
- Rate and rhythm disorders;
- Supraventricular arrhythmias;
- Ventricular arrhythmias.

Note that more than one of these items can be ticked.

Population: safety.

**12.3.7. Analysis tables for the whole 24 weeks period**

Repeat tables, population=safety, with the adapted treatment groups focusing on subjects who used GLPG0634 during both study periods:

**Table 14.3.3.7: ECG over the whole study: Descriptive statistics of the actual values per time point****Table 14.3.3.8: ECG over the whole study: Descriptive statistics of the changes from baseline****Table 14.3.3.9: ECG over the whole study: Shift table of the QT abnormalities****Table 14.3.3.10: ECG over the whole study: Treatment-emergent QT abnormalities****Table 14.3.3.11: ECG over the whole study: Treatment-emergent abnormal change in QT****Table 14.3.3.12: ECG over the whole study: Frequency table of the eCRF ECG interpretation per time point**

### 12.3.8. Figures

No figures planned.

### 12.3.9. Listings

#### Listing 16.2.12.1: ECG: Full listing

Listing per treatment group, per subject and per time point of the ECG parameters (raw values as well as changes from baseline), flagging abnormal results. Includes the ECG interpretation and morphology findings.

Population: safety.

#### Listing 16.2.12.2: ECG: Abnormalities listing

Listing per treatment group, per subject and per time point of all post-baseline data scored as out-of-normal-range or clinically significant, plus also the baseline reference time point.

Population: safety.

## 12.4. VITAL SIGNS

### 12.4.1. Available Data

Available parameters: pulse rate, diastolic and systolic blood pressure, temperature.

### 12.4.2. Baseline and Change from Baseline

The baseline value will be the last nonmissing value prior to first dosing. Baseline will be determined per vital signs parameter individually. It is recognized that baseline parameters may thus come from more than one vital signs reading and not just from the “baseline visit” reading.

The change from baseline will be calculated for all post-baseline time points as:

Change from baseline at time point t = value at time point t – baseline value.

### 12.4.3. Normal Ranges

Parameter, unit	Normal range	
	Lower limit	Upper limit
Pulse, bpm	40	100
DBP, mmHg	45	90
SBP, mmHg	90	140
Temperature, °C	35.5	37.5

Values equal to the boundaries are still considered normal (N). A value is classified as abnormally low (L) when the value < lower limit of the normal range. A value is classified as abnormally high (H) when the value > upper limit of the normal range.

#### 12.4.4. Last on-treatment result

Derived per parameter separately, for values as well as abnormalities.

Three last on-treatment determinations will be done, depending on the chapter of analysis:

1. Including all nonmissing post-baseline values, including “use=No” and unscheduled measurements, up to and including the Week 12 value.
2. Including all nonmissing post-Week 12 values, including “use=No” and unscheduled measurements, up to and including the Week 24 value.
3. Including all nonmissing post-baseline values, including “use=No” and unscheduled measurements, up to and including the Week 24 value.

Early discontinuation visits are considered as on-treatment visits as well.

#### 12.4.5. Worst-Case Abnormality

Derived per parameter separately, for abnormalities only.

Three worst-case determinations will be done, depending on the chapter of analysis:

1. Including all nonmissing post-baseline values, including “use=No” and unscheduled measurements, up to and including the Week 12 value. Also including the follow-up value in case the subject did not participate in the second period of the study. If the subject participated in the second period of the study, then the follow-up value will be included in the worst-case of the second period of the study, not of the first period.
2. Including all nonmissing post-Week 12 values, including “use=No” and unscheduled measurements, up to and including the follow-up value.
3. Including all nonmissing post-baseline values, including “use=No” and unscheduled measurements, up to and including the follow-up value.

Possible categories:

- H = abnormally high: at least one postdose measurement is above the normal range, and there are no values below the normal range.
- L = abnormally low: at least one postdose measurement is below the normal range, and there are no values above the normal range.
- H+L = abnormally high and low: at least one postdose measurement is above the normal range, and at least one other postdose measurement is below the normal range.
- N = normal: all postdose measurements are within normal limits.

#### 12.4.6. Tables up to Week 12

No formal inferential statistics (p-values) will be derived. Time points to present: screening, baseline, Weeks 1-2-4-8-12, last on-treatment, worst case.

If the subject did not participate in the second period of the study, then the follow-up visit will be presented in the table of the first period of the study. If the subject participated in the

second period of the study, then the follow-up value will be presented in the table of the second period of the study, not of the first period.

**Table 14.3.4.1: Vital signs up to Week 12: Descriptive statistics of the actual values**

Descriptive statistics of the actual values per test and unit, treatment group and time point.

Population: safety.

**Table 14.3.4.2: Vital signs up to Week 12: Descriptive statistics of the changes from baseline**

Descriptive statistics of the changes from baseline per test and unit, treatment group and time point. The actual value at baseline will also be presented in this table.

Population: safety.

**Table 14.3.4.3: Vital signs up to Week 12: Summary table of means**

Summary table per test and unit, treatment group and time point, showing only the mean value of actual values and changes from baseline.

Population: safety.

Table to be created for the Week 12 interim analysis as well.

**Table 14.3.4.4: Vital signs up to Week 12: Shift table of the abnormalities per time point**

Shift table per test, treatment group and time point. The table will present the shift in abnormality (L/N/...) for “last” and “worst-case” versus the baseline abnormality (L/N/H).

Population: safety.

**Table 14.3.4.5: Vital signs up to Week 12: Treatment-emergent abnormalities per time point**

Frequency table of the treatment-emergent abnormalities per parameter, treatment group and time point (including the worst-case). A post-baseline abnormality is considered treatment-emergent if it is different from the baseline result.

Population: safety.

## **12.4.7. Tables over the whole 24 weeks period**

The same tables again, but with adapted treatment groups focusing on the subjects who used GLPG0634 during both study periods. Time points to present: screening, baseline, Week 1-2-4-8-12, last on-treatment during period 1, worst case during period 1, Weeks 16-20-24, last on-treatment during period 2, last on-treatment during the whole study, follow-up (all follow-up visits in the study), worst case during period 2, worst case during the whole study.

Population: Safety.

**Table 14.3.4.6: Vital signs over the whole study: Descriptive statistics of the actual values**

**Table 14.3.4.7: Vital signs over the whole study: Descriptive statistics of the changes from baseline**

**Table 14.3.4.8: Vital signs over the whole study: Summary table of means**

**Table 14.3.4.9: Vital signs over the whole study: Shift table of the abnormalities per time point**

**Table 14.3.4.10: Vital signs over the whole study: Treatment-emergent abnormalities per time point**

## 12.4.8. Figures

No figures are planned.

## 12.4.9. Listings

### Listing 16.2.13.1: Vital signs: Full listing

Listing per treatment, per subject and per time point of all parameters: raw values, changes from baseline, and flagging abnormal results.

Population: safety.

### Listing 16.2.13.2: Vital signs: Abnormalities listing

Listing per treatment group, per subject and per time point of all post-baseline data scored as out-of-normal-range or clinically significant, plus also the baseline reference time point.

Population: safety.

## 12.5. PHYSICAL EXAMINATIONS

### Listing 16.2.14: Physical examinations: Abnormal findings

Listing per treatment group, per subject and per time point of the selection of all abnormal findings (i.e., “abnormal” or “changed”).

Population: safety.

## STATISTICAL ANALYSIS PLAN HISTORY

SAP / Amendment #	Date	Version
Statistical Analysis Plan-Addendum	13-Jun-2016	Version 1.0
Statistical Analysis Plan-Addendum v2.0	20-Jul-2016	Version 2.0: In section “Step 3: Correlation of each individual biomarker versus week 12 efficacy and safety”, supporting tables were added to the plots to display the Pearson or point-biserial correlation coefficients. In section “Step 4: Biomarkers predicting the Week 12 Efficacy and Safety”, baseline value of the efficacy or safety parameters will be added as covariate in the ANCOVA model expect for ACR-N parameters.

## 1. INTRODUCTION

This document is an addendum to the main study SAP version 5.00. It is intended to define the statistical analysis of the additional pharmacodynamics measurements.

This Addendum to the final SAP was written after database unblinding and after viewing the main study results.

## 2. PD POPULATIONS

The PD population will be a subpopulation of the ITT from the main study analysis:

- All randomized subjects who received at least one dose of study medication and have at least one post-Baseline efficacy assessment. This is the ITT population in the main study analysis, available in ADaM.ADSL variable ITTFL.
- The 50 mg/day dose groups will be excluded (no PD samples analyzed for these groups; and still excluded from PD population if by accident there would be a result from a 50 mg/day subject).
- Also subjects who have no PD results (eg not allowed to analyze as per subject ICF version) will be excluded from this analysis.

The analysis population will always be indicated in a subtitle in the table, listing or figure.

## 3. TREATMENT GROUPS

### 3.1. RANDOMIZED VERSUS ACTUAL TREATMENT

For efficacy and PD parameters, the treatment group as assigned by the randomization will be used in the analysis (i.e., as-randomized analysis).

### 3.2. TREATMENT GROUP LABELS

The following treatment group labels will be used in the tables, listings and figures:

- Placebo
- GLPG0634 100 mg q.d.
- GLPG0634 200 mg q.d.
- GLPG0634 50 mg b.i.d.
- GLPG0634 100 mg b.i.d.

The 50 mg q.d. and 25 mg b.i.d. groups will not be used (because PD samples are not analysed).

## 4. ANALYSIS PERIODS AND ANALYSIS TIME POINTS

### 4.1. RELATIVE NUMBER OF DAYS

The relative day (DY) is calculated as follows:

= Visit date – reference date + 1 day, when the visit date is on or after the reference date

= Visit date – reference date, when the visit date is before the reference date.

The reference date in the study is the first study medication intake date, which by definition has DY=1. There is no DY=0.

## 4.2. ALGORITHM OF ALLOCATING VISITS TO TIME WINDOWS

The main study analysis used the following time windows:

All visits (including early discontinuation visits and unscheduled visits but excluding visits without data) will be placed into time windows according to their relative day (DY) in the study, according to the following allocation table:

Time point label	Target day	Interval lower bound	Interval upper bound
Screening (3)	NA	NA	NA
Baseline (1)	NA	NA	NA
Week 1	8	2	11
Week 2	15	12	21
Week 4	29	22	42
Week 8	57	43	70
Week 12	85	71	98
Week 16	113	99	126
Week 20	141	127	154
Week 24	169	155	182
>Week 24 (2)	NA	183	+∞
Follow-up (3)	7-10 days after last visit	NA	NA

(NA = not applicable).

### Notes:

- (1) The actual baseline reference value will be determined per parameter as the last available pre-dosing data point, so might differ from this “baseline” visit interval. There will be only one baseline time point in this study: the last non-missing value prior to first dosing of study drug.
- (2) Visits falling really late in the study (relative day > 182; excluding the follow-up visit) will be allocated to a “>Week 24” interval, and will not be shown in tables nor figures, but will only be listed.
- (3) For the screening and follow-up visits, no time window is defined. The visit as recorded in the eCRF will be used. Follow-up visits of subjects who discontinue the study prior to the Week 12 re-randomization will be shown separately as well in the tables that present the first part of the study only. For tables that present the study as a whole, all follow-up visits will be shown.

Tables, figures and listings will present the time points, not the visits.

For this additional PD analysis, only Baseline, Week 4 and Week 12 samples will be analyzed. These will be placed into the above time windows to allow a matching with the main analysis. If a PD result ends up in an analysis visit different from “baseline”, “week 4” and “week 12”, then it will not be used in the tables and figures.

## 4.3. SELECTION OF VISITS

It is possible that more than one visit gets allocated into the same time window. In that case, only one visit will be selected for tables and figures. The non-selected visit(s) will only be listed and flagged as use=no.

The visit with a relative day (DY) closest to the target day will be selected. If there are multiple visits at the same distance of the scheduled visit day (meaning: equal  $ABS(DY - \text{target day})$ ), then the one latest in time is selected.

In case more than one parameter is measured per time point, the selection is performed per parameter and per time point, not per “sample” and per time point. Missing values are removed before the selection is made.

## **5. HANDLING OF DATA**

### **5.1. CALCULATION OF DESCRIPTIVE STATISTICS**

For continuous parameters, descriptive statistics will be presented when  $N \geq 2$ . When  $N=1$ , the observation will not be shown in the table but only in the listing.

Descriptive statistics will include at least the following:

- the number of non-missing data points (N)
- the number of values above the lower limit of quantification and below the upper limit of quantification (only applicable to tables of actual values)
- the arithmetic mean
- the geometric mean (only applicable to tables of actual values)
- the standard error (SE) and the standard deviation (SD)
- the median, minimum and maximum
- 95% confidence interval of the mean (only when requested).

### **5.2. CALCULATION OF PERCENTAGES**

Missing values will not be included in the denominator count when computing percentages.

### **5.3. HANDLING OF VALUES BELOW (OR ABOVE) A THRESHOLD**

Values below the detection limit (“BLQ”, “<x” or “OOR <”) will be imputed by a value of “0.1”. Note that the central lab was unable to provide a value for the LLOQ.

Values flagged as extrapolated (ie, a result flagged with an asterisk) in the transfer from the bioanalysis lab will be handled as if they are BLQ, and will be imputed by “0.1” as well.

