### 8.1. PD PARAMETERS

The raw PD markers will be provided by the bioanalysis lab: GM-CSF, IFN $\gamma$ , IL-1 $\beta$ , IL-2, IL-4, IL-5, IL-6, IL-7, IL-8, IL-10, IL-12 (p70), IL-13, IL-17A, IL-21, IL-23, MIP-1 $\alpha$ , MIP-1 $\beta$  and TNF- $\alpha$ . All results are expressed in pg/mL. The raw values (with their unit) will be used in the analysis without any transformation or manipulation (except for the imputation of values BLOQ or missing values).

Analysis will show actual values, changes from baseline and percent changes from baseline.

%change from baseline = 100 x (change from baseline) / baseline, and is only defined when the baseline  $\neq$  0.

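### The PD addendum sets every extrapolated result to 0.1 pg/mL with no direction stated, and keeps an imputed 0.1 baseline as the denominator of percent change

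*SAP*

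**What the plan says.** The SAP addendum defines extra analyses of 18 cytokines and chemokines at baseline, Week 4 and Week 12.

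- **Low results.** Section 5.3 lists three codes, all low-side (`BLQ`, `<x`, `OOR <`), and such results "will be imputed by a value of “0.1". It adds: "Note that the central lab was unable to provide a value for the LLOQ".
- **Extrapolated results.** The next paragraph covers any result carrying an asterisk from the laboratory; these "in the transfer from the bioanalysis lab will be handled as if they are BLQ, and will be imputed by" 0.1 as well. It does not say which end of the curve an asterisk refers to.
- **High results.** The section is headed "HANDLING OF VALUES BELOW (OR ABOVE) A THRESHOLD", but no rule for the upper end follows. Section 5.1 nevertheless asks for "the number of values above the lower limit of quantification and below the upper limit of quantification", and Table PD 1 carries the matching footnote.
- **Scale.** Section 8.1 states: "All results are expressed in pg/mL", so the constant is 0.1 pg/mL for every marker. It also states: "The raw values (with their unit) will be used in the analysis without any transformation or manipulation", apart from imputation. Percent change is undefined only when the baseline is zero.

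For comparison, the main SAP's rule for safety data (section 4.3.1) works in both directions: a value above the limit takes the limit. Its rule for PD data (section 4.3.3) uses half the detection limit for low values.

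**The concern.** There are two separate problems.

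First, a programmer who follows section 5.3 literally must give 0.1 to any asterisked result, including one extrapolated beyond the top of the curve. A high follow-up reading would then look like a near-total fall, and a high baseline reading like a near-zero starting point. This would reach the absolute-change ANCOVA (Tables PD 4, PD 5 and PD 9, which also use baseline as a covariate), the correlations in Step 3 and the prediction models in Step 4.

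Second, even if asterisks mark only the low end, a baseline replaced by 0.1 is not zero, so it remains as the denominator of percent change. The 0.1 is tied to no stated assay limit. The size of the percent change then reflects the chosen constant more than the measurement. This reaches Tables PD 3 and PD 8, the percent-change plots and correlations, and the models in Tables PD 12, PD 15 and PD 18.

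**Working it through.** **Inputs from the addendum.** Constant 0.1 (section 5.3); unit pg/mL, no transformation, and percent change = 100 x (follow-up - baseline) / baseline (section 8.1). The documents do not derive the 0.1, so there is no stated figure to reproduce. They give no concentrations and no PD arm sizes. Every concentration below, and the arm size, is therefore an assumption used for illustration.

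**1. A high-end extrapolation coded as 0.1 (only if asterisks can mark the high end).**

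- Baseline 2, Week 12 reading 500. As reported: 500 - 2 = +498, and 100 x 498 / 2 = +24,900%. As coded: 0.1 - 2 = -1.9, and 100 x (-1.9) / 2 = -95%.
- For other baselines with a follow-up coded 0.1, the recorded percent change is -98% from 5, -99% from 10 and -99.9% from 100.
- High reading at baseline instead: 1000 falling to 800 is -200, or -20%. With the baseline coded 0.1 it becomes 800 - 0.1 = +799.9, or +799,900%.

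In each case the sign is reversed, in absolute as well as percent change.

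**2. A low baseline coded as 0.1 (whatever the asterisk means).**

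| Assumed follow-up (pg/mL) | Percent change from 0.1 |
|---|---|
| 0.5 | +400% |
| 1 | +900% |
| 1.1 | +1,000% |
| 5 | +4,900% |
| 10 | +9,900% |
| 100 | +99,900% |

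Four-figure percent changes therefore need a follow-up of at least 1.1 pg/mL.

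**3. Dependence on the constant, assumed follow-up 5.**

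| Constant | Absolute change | Percent change |
|---|---|---|
| 0.05 | 5 - 0.05 = 4.95 | 100 x 4.95 / 0.05 = +9,900% |
| 0.1 | 5 - 0.1 = 4.9 | 100 x 4.9 / 0.1 = +4,900% |
| 0.5 | 5 - 0.5 = 4.5 | 100 x 4.5 / 0.5 = +900% |

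The percent change varies elevenfold (9,900 / 900), while the absolute change moves by 0.45 pg/mL.

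**4. Effect on an arm mean.** Suppose all subjects in an arm of n change by -20%, except one who goes from 0.1 to 5. The mean shifts by (4,900 + 20) / n = 4,920 / n points. At n = 85, the planned randomised arm size, that is 57.9 points, from -20% to +37.9%. Five such subjects give (5 x 4,900 + 80 x (-20)) / 85 = +269%. The PD population excludes subjects without PD results, so n may be smaller and the shift larger.

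**The case against.** The strongest reply is that the rule may be coherent as written. Section 5.3 names only low-side codes, then treats extrapolated results like them, which fits an asterisk that marks low-end extrapolation only. The upper-limit count is weak evidence to the contrary: the same line counts results above a lower limit that the laboratory could not supply, so it may be template text. This stands. No part of the documents says that asterisked results include high readings, so the sign reversal is conditional.

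The reply on impact also stands in part. Comparisons with placebo and between regimens use absolute change, where the choice of low-side constant matters little; percent change is not tested between arms. Medians, ranges and box plots are planned, with geometric means for actual values, and the count of quantifiable results shows how often substitution occurred. However, the correlations and models do not use medians. The repeat without outliers in section 5.5 is optional and has no definition of an outlier. A high reading coded 0.1 would sit among the BLQ values, where outlier screening would not be expected to find it.

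A reader might infer that high readings will become the lowest values in the dataset, that percent changes in the thousands will occur, and that the between-arm contrasts will be driven by coding. The documents do not support any of these as fact. The flag definition and the concentrations are not given, and with no lower limit stated, measured values below 0.1 cannot be excluded.

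**Conclusion.** The point holds in two parts of different strength.

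- **Direction of extrapolation: conditional.** The text gives 0.1 to every asterisked result and leaves above-range values without a rule. If any asterisk marks the high end, a rise is recorded as a near-total fall in the ANCOVA, the correlations and the prediction models. If asterisks mark only the low end, no reversal occurs and one sentence saying so settles that part; values above range would still lack a rule.
- **Percent-change denominator: unconditional as a defect of the rule.** Wherever a baseline is set to 0.1, the percent change is governed by an arbitrary constant. How often this happens, and how large the figures become, depends on concentrations that the documents do not give. It does not affect the between-arm ANCOVA on absolute change.

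The priority is low. The addendum was written after unblinding and describes its own analyses as post-lock. They are exploratory, and the primary endpoint is unaffected.

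**What to change.** 1. Obtain a direction flag from the laboratory for extrapolated results, and limit the 0.1 imputation in section 5.3 to results out of range on the low side.
2. Add a rule for the high side: keep the reported value, or cap it at the highest quantifiable value. Keeping it retains a figure the laboratory marked as extrapolated; capping needs an upper limit that the documents do not give, so the same query should ask for it.
3. In section 8.1, set percent change to missing when the baseline is BLQ or imputed, and report how many subjects this removes.

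The cost is a laboratory query, a few lines of addendum text and fewer subjects in the percent-change outputs.

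Log-scale analysis is optional and is a trade-off. It tames high values but is more sensitive to the low-side constant: for a follow-up of 5, the ratio to baseline is 5 / 0.05 = 100 with one constant and 5 / 0.5 = 10 with another. If logs are used, the analysis should be repeated with a second constant.
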